The investigational device is a separate module, inhalation app-module, embedded in the Cloud-based CE-marked system called AsthmaTuner. Our hypothesis is that provided education and training with the medical device measurement will improve the patients' ability to correctly use their inhalers over time. Thus, the aim of this study is to assess the effect of app-based medical device for education and training on inhalation techniques at 6-12 weeks follow-up visit in subjects with asthma and COPD. Secondary aim is to evaluate if the medical device is feasible to use in clinical practice. The study endpoints are peak inspiratory flow (PIF), time to PIF, flow (litre per min), inhalation time (seconds) and breath hold (seconds) divided by DPI and MDI, together with assessment of how the patient handles their inhaler according to a set of critical criteria. Patients treated for COPD or asthma in primary or secondary care will be invited to participate in a two-armed stratified randomised controlled blinded study (RCT) over 6-12 weeks.

The patient will download AsthmaTuner to their smartphone that connects to a Bluetooth spirometer (in this study, MIR AsthmaTuner). Inhalation test through Airflow Trainer, an adjustable resistance mounted on the home spirometer (Airflow Trainer), determines if the inhalation flow agrees with the endpoints for the inhaler used by study subject. The expected results of this trial will allow us to determine if app-based inhalation device improves inhalation technique compared with standard care. The goal of this project is to provide sufficient information for a CE-marked product of the inhalation app-module. The study will be performed by Karolinska Institutet (KI), [name] research group, also being the sponsor, but supported technically and intellectual expertise from Astra Zeneca and MediTuner AB (the owner of AsthmaTuner).

A.1.2 Identification of the clinical investigation plan

Title: App-based medical device for education and training of inhalation technique

Acronym: APPETITE

(Svensk titel): App-baserad medicinteknisk produkt för utbildning och träning av inhalationsteknik

Clinical investigation plan code: 02

CIV-ID: 23-06-043273

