11	For Handyhaler or similar, check powder drug rests in capsule, if necessary, inhale again	Breathed out and away from the mouthpiece of the inhaler

Each subject in both intervention and control arm will receive standard assessment and instruction on inhalation technique according to criteria in Table 2 at baseline visit. The study endpoints will be collected at the follow-up visit (6-12 weeks).

Randomisation and masking

Each of the 80 subjects is stratified to block of 4 numbers according daily used inhaler of (1) DPI, (2) MDI or (3) both MDI/DPI. Simple randomisation (1 to 1) will be applied in each block and at each study site. The randomisation will be blinded for the evaluator at 6-12 week visit, which practically means that not the same study personnel will do the baseline randomisation and the final 6-12 weeks assessment of inhalation technique.

Endpoints

Primary endpoint is number of subjects presenting successful inhalation techniques as defined by objective endpoints divided by:

- DPI: PIF \geq 30 L/Min, time to PIF <0.5 seconds measured with the investigational device.
- MDI: inspiration time (> 3 seconds) and PIF less than 60 L/Min measured with the investigational device.
- Together with subjective critical endpoints at 6–12-week follow-up visit, assessed by study personnel, Table 2.

Secondary endpoints:

- Feasibility and safety of using the investigational device for education and training of inhalation technique based on questionnaire and interviews from subjects and healthcare personnel, Appendix 3.

Study personnel will get access and be trained in methods and procedures for informed consent, randomisation, investigational device, data collection and documentation. The study endpoints will be documented in electronic Case Report Form (CRF) provided by Karolinska Institutet. Data analysis will start as soon as all 80 included subjects have completed or considered to be lost to follow-up at 6-12 week's visit by local investigator.

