Informed consent	X	
Randomization	X	
Questionnaires of medical history and usability	X	X
Spirometry test	X	
Standard review and correction of inhalation technique	X	X
Objective assessment of inhalation technique		X
Adverse events or device deficiency		X

Randomisation

Computer-based randomisation stratified for subjects' daily inhaler use into three groups of DPI, MDI or both DPI and MDI devices of four block numbers in each stratum per investigational site.

Interview and electronic questionnaires

- A structured health questionnaire completed at the first visit will provide information regarding medical history, health care utilization and experiences of inhalation education and training, Appendix 4.

Dynamic spirometry

- The lung function test will measure forced expiratory flow in one second (FEV₁), forced vital capacity (FVC), and FEV₁/FVC according standardised procedures [31]. Applied percent of predicted reference values, adjusting for age, sex, height, weight and ethnicity, will be calculated based on continuous prediction equations of normal population [32].

Standard review of inhalation technique

- All subject's ability to handle their inhaler(s) and inhalation technique will be reviewed and corrected at baseline visit and assessed at 6–12-week follow-up visit according to endpoints in Table 2.

Investigational device - app-based intervention for education and training of inhalation technique

1. Subjects randomised to intervention will receive instructions on using the investigational device, accompanied with written information (instructions for use) from study personnel at baseline visit. The subjects are instructed to use the investigational device 3-7 times per week to achieve the maximal effect.

2. Instruction for use manual on how to use medical investigational device will be available for subjects and study personnel at investigational sites (Appendix 5). Briefly, subjects follow the following procedure:
 - a. Baseline visit: Download (Apple Store or Google Play) and login with BankID or similar to the AsthmaTuner app. Automatic Bluetooth connection will be established between the MIR AsthmaTuner and the app.
 - b. Study personnel at Karolinska institutet set up login through BankID or SITHS card to AsthmaTuner Careportal for study personnel at investigational site.
 - c. Enter patient information: Fill out patient's initial letters, study ID, height, weight and type of inhaler. Press "next" to start the test.

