The monitor and possible authorities must be given direct access to source documents (original documents, data and records). Direct access includes permission to examine, analyse, verify and reproduce any record(s) and report(s) that are important to the evaluation of the clinical study. In order to be able to do that, a written consent from each patient should be obtained. Additionally, a secrecy agreement between the monitor and the person responsible for patient records at the study site will be signed.

A.7 Statistical considerations

The analytical approach of this RCT is intention-to-treat, analyzing the effect of the investigational device across all randomized subjects with assessed inhalation technique at the 6–12-week follow-up visit. Additionally, a per-protocol analysis will be conducted on subjects who performed an inhalation test on average more than once per week during the study period, to evaluate the efficacy of education and training on inhalation technique between the intervention and control groups.

The null hypothesis of this investigation is no difference in success rate of inhalation technique between subjects assigned to intervention or control group. If the number of patients with inhalation technique deemed for correction differ significantly between intervention and control group at 5% significance level, the null hypothesis will be rejected. Based on our cross-sectional pilot study, 50% of in 40 patients with asthma demonstrated successful inhalations technique (Appendix 3), assuming +25% absolute change of correct inhalation technique in the intervention group compared with control group including 20% drop out rate, enrolment of at least 80 patients will be sufficient to reach 80% power at 5% significance level.

Primary analysis: The success rate of subjects with correct inhalation technique according to objective and subjective critical endpoints at the 6-12 weeks follow-up visit. The effect of the medical device on rate of successful inhalation technique will be determined across randomisation groups with logistic regression analysis as risk ratio (RR) with 95% confidence interval. No interim analysis will be performed.

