Secondary analyses: The analysis of feasibility and the experienced benefit of inhalation education and training support will be estimated on a Likert scale from 1 (not at all) to 5 (strongly agree), and summarized as mean and median scores. Quality content analysis will assemble collected information from questionnaire and interviews of respiratory nurses together with comments from patients. Data will be presented as categories based on oral or written quotes.

Sensitivity analysis: Analyse the rate successful inhalation technique based on objective and all subjective (not only critical) endpoints.

Descriptive statistics of the study population will be presented across the randomisation groups including information of number of randomised subjects, sex, age, asthma/COPD diagnosis, tobacco smoking status, educational level and type of inhaler(s) used for daily treatment.

The purpose of stratified block randomisation per investigational site is to adjust for imbalance in subjects' acquired knowledge of inhalation technique, common errors related to DPI and MDI devices and assessor's review of inhalation technique.

The study and the data management will be monitored by CRO, Karolinska Trial Alliance. In addition, two independent researchers ([name] and [name]) will have full access to all study information for study quality evaluation.

A.8 Data management

A CRF is used for data collection, Appendix 7. Clinical data will be entered directly into the validated electronic CRF of Research Electronic Data Capture (REDCap), stored at Karolinska Institutet, by the study personal at each site. The REDCap CRF is an online password protected database provided for the KPE Lung and Allergy department, QB:84, by Karolinska Institutet. The data entered the CRF will be validated before the clinical investigation begins.

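### A.7 credits the site and inhaler strata with adjusting for prior knowledge of technique, which they do not measure; the baseline technique review should be recorded before randomisation and used as a covariate

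*Protocol*

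**What the plan says.** - **Purpose of stratification (A.7).** Stratified blocks per site have a purpose that "is to adjust for imbalance in subjects' acquired knowledge of inhalation technique". The sentence goes on to name errors typical of each inhaler class and the assessor's review. A.6.1 adds that the scheme will balance confounders.
- **Strata (A.6.1, A.6.4).** Subjects are "stratified for subjects' daily inhaler use into three groups of DPI, MDI or both DPI and MDI devices", in blocks of four within each site. No stratum is based on technique or knowledge.
- **Baseline technique (A.6.4).** Handling and technique "will be reviewed and corrected at baseline visit" in every subject, using the Table 2 criteria. In Table 3 this review is marked at both visits. The row "Objective assessment of inhalation technique" is marked at follow-up only.
- **Hypothesis.** A.1.1 expects that the device "will improve the patients' ability to correctly use their inhalers over time". The formal null in A.7 is "no difference in success rate of inhalation technique between subjects assigned to intervention or control group".
- **Analysis (A.7).** The primary model is logistic regression across arms, reported as a risk ratio; no covariate is named. The listed descriptive characteristics do not include baseline technique.
- **Eligibility (A.6.3).** Daily DPI or MDI users aged 16 or over may enter, whatever their technique.

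**The concern.** The protocol names prior knowledge of technique as an imbalance to be dealt with, then assigns the task to strata that do not contain it. Two DPI users at one site, one competent and one not, fall in the same stratum. The blocks do nothing to spread such subjects evenly between the arms.

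Technique at entry is plausibly the strongest predictor of technique at follow-up. In a trial of 80, the share already competent can differ noticeably between arms by chance. A reader would then not know how far an observed difference reflects the starting position. Nor could a reader tell whether the app helped failing users or kept competent ones from lapsing. Table 1 notes that errors often return 4 to 6 weeks after training, so both are credible routes to benefit.

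The information is nearly free, because the Table 2 review is already carried out at baseline. The stated design uses it to teach and correct, and gives it no role in the strata, the primary model or the listed baseline characteristics.

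**Working it through.** **Inputs from the protocol.** N = 80 allocated 1:1, so 40 per arm. With the 20% dropout in A.7, 80 × 0.8 = 64, so 32 per arm. Planned success is 50% against 75%.

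**Assumptions.** The share correct at baseline is 50%, the pilot figure in A.7; 30% and 70% are also shown. The association between baseline and follow-up success is 20, 40 or 60 points; the protocol gives no figure. Strata are taken as uninformative about technique, so the imbalance probabilities are upper-end values.

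**The plan's own figure.** The plan gives no figure for balance on technique. Its sample size does not reproduce: a two-sided 5% test with 80% power for 50% against 75% needs

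(1.960·√(2·0.625·0.375) + 0.842·√(0.25 + 0.1875))² / 0.25² ≈ 57.7, so 58 per arm, 116 in total, and 116/0.8 = 145 with dropout.

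Power is 0.64 at 40 per arm and 0.54 at 32. That is a separate matter. It matters here because it explains why the power figures below start near 0.65, and because small arms make chance imbalance larger.

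**Step 1: size of chance imbalance.** The SD of the between-arm difference in baseline success is √(2·0.5·0.5/m), which is 11.2 points at m = 40 and 12.5 points at m = 32. Exact enumeration of two independent binomials gives the probability of an imbalance in either direction:

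| Share correct at baseline | Per arm | ≥10 points | ≥15 points | ≥20 points |
|---|---|---|---|---|
| 50% | 40 | 0.43 | 0.22 | 0.09 |
| 50% | 32 | 0.38 | 0.26 | 0.10 |
| 30% or 70% | 40 | 0.39 | 0.18 | 0.07 |
| 30% or 70% | 32 | 0.34 | 0.22 | 0.08 |

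The lower 10-point value at 32 per arm comes from the discrete scale: the smallest qualifying gap is 4/32 = 12.5 points, against 4/40 = 10.

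**Step 2: effect on the observed difference.** Shift = imbalance × association. For 15 points: 0.15 × 0.20 = 3 points, 0.15 × 0.40 = 6 points, 0.15 × 0.60 = 9 points, against a planned 25.

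**Step 3: effect on the test.** In 40,000 simulated trials per scenario, control success was 50% on average, split by baseline status. The app arm was raised to 75% by a common shift on the logit scale. An unadjusted two-proportion test was compared with a Mantel-Haenszel test stratified on baseline success.

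| Association | Power at 40 per arm, unadjusted → stratified | Power at 32 per arm, unadjusted → stratified |
|---|---|---|
| 20 points | 0.65 → 0.66 | 0.56 → 0.56 |
| 40 points | 0.65 → 0.70 | 0.56 → 0.61 |
| 60 points | 0.65 → 0.79 | 0.56 → 0.69 |

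Under the null, the unadjusted test rejected in about 6% of all trials. At 40 per arm, the app arm started at least 15 points ahead in about 11% of trials. Among those trials it rejected in 7%, 10% and 15% for the three associations; the stratified test stayed between about 4.5% and 6%.

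**The case against.** **The comparison is valid as planned.** The aims in A.5 and the null in A.7 compare arms at follow-up, and randomisation supports that comparison without any baseline value. The 5% test and the confidence interval already allow for chance imbalance, which is as likely to work against the device as for it. This stands. A reader might infer from the wording in A.1.1 that the trial must show change from baseline, or that the primary result is systematically biased. The documents support neither: the first rests on introductory wording, and the second confuses conditional with systematic bias.

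**Covariates and forms may be settled elsewhere.** Covariates are commonly left to a statistical analysis plan, the A.7 descriptive list need not be exhaustive, and the CRF (Appendix 7) is not shown. A.8 sends subjective endpoints straight to the CRF, so the baseline review may already be captured. It therefore cannot be said that the final report would be unable to show baseline balance. What remains is that A.7 attributes a property to the strata that they do not have, and that the procedures do not require a rating before correction.

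**The strata are not useless.** They directly serve the other two purposes in the A.7 sentence. Sites span primary and secondary care and may partly reflect prior education. The baseline questionnaire asks about experience of inhalation training. These are proxies and leave variation within strata untouched.

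**The size is uncertain.** A.3 describes the pilot as 40 schoolchildren, whereas this trial takes subjects from 16 years, and A.7 uses the 50% to set the control rate. Correcting everyone at baseline may weaken the association. At 20 points, adjustment gains almost nothing.

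**Conclusion.** The point holds as a recommended improvement and a needed correction of wording. The strata balance site and inhaler type; balance on technique is at best indirect. The cost is lost precision, conditional bias and weaker interpretation. The trial's primary comparison is not invalid.

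With 50% assumed competent at entry, about one trial in five (22%) at 40 per arm, or one in four (26%) at 32, would have a gap of 15 points or more. The resulting shift of 3 to 9 points and the power gain of about 0.01 to 0.14 at 40 per arm depend wholly on the assumed association. The power gain was computed with a stratified test, not the planned logistic model.

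Attrition adds a reason to record the value. Subjects who miss the follow-up window are withdrawn from the primary analysis (A.6.1, A.6.3), so the analysed arms are not exactly the randomised arms. A baseline rating would let the report show how comparable they are.

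**What to change.** 1. In A.6.4 and Table 3, require the Table 2 critical-step result (pass or fail) for each inhaler to be recorded at the baseline visit in all subjects, before randomisation and before any correction. Both conditions matter: review and allocation occur at the same visit and only the follow-up evaluator is blinded, so a rating made after allocation could itself be biased.
2. In A.7, include baseline critical-step success as a prespecified covariate in the primary model, together with the stratification factors, and state how the risk ratio is derived from that model.
3. Report baseline critical-step success by arm in the baseline table.
4. Reword the A.7 sentence to say that the strata balance site and inhaler type, and that baseline technique is handled by adjustment.

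**Cost.** The review must come before the allocation call and be entered in the CRF, if it is not captured already. One model term is added; no visit or procedure is. The limitation is that only the subjective half of the endpoint is covered, because no objective measurement is scheduled at baseline.
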